## 2.0 OBJECTIVES

### 2.1 Primary Objectives:

- To assess the validity of BIS as a tool for quantification of lymphedema through comparison with perometry
- To determine relationship between impedance ratios, relative volume changes (RVC), and self-reported symptoms

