## 6.0 STATISTICAL ANALYSIS

### 6.1 Primary and Secondary Endpoints

The primary aims of the study are to assess the validity of BIS measurements by comparison with perometry and determine the relationships of BIS measurements to perometer measurements and to self-reported symptoms. The secondary aims will be to compare diagnostic criteria for lymphedema for each assessment method, assess the natural history of lymphedema using BIS, and determine a threshold for intervention using BIS. Thus primary endpoints will subsist in volumetric and BIS measurements of each arm at the baseline examination and during follow-up visits, as well as data captured by LEFT-BC questionnaires. The changes of arm volumes will be quantified using established RVC formula (26), and we will use a similar formula for quantification of BIS changes after evaluating the statistical distribution of BIS measurements.

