### 6.2 Sample Size and Statistical Power

The sample size will be determined with the prospect of primary aim of this study, i.e, to evaluate the correlation between arm volume changes measured by perometry and quantified using RVC formula (26) and using relative changes of impedance measured by biimpedance spectroscopy (BIS). We want to evaluate this correlation for all subjects enrolled, and separately, for a subgroup of those subjects who develop lymphedema with  $RVC \geq 5\%$ . The first analysis will evaluate overall agreement between these two techniques and the second analysis will evaluate agreement between assessment of lymphedema grade by both techniques. We plan to quantify the relationship between these two measurement methods using Kendall's tau coefficient (34).

We chose to use a non-parametric correlation coefficient to account for a possible non-linear form of the relationship between the two measurements, and for a possible non-normal distribution of BIS measurements. We expect a moderately high correlation between these measurements,  $\tau = 0.50$ . The choice of sample size is motivated by a need to evaluate the correlation with sufficient precision rather than by a hypothesis test: we want to obtain a lower bound of 95% confidence interval for the estimate of tau of no less than 0.2 in the LE group and of no less than 0.42 overall. We assume that 10% of enrolled subjects will develop lymphedema with  $RVC \geq 5\%$ . Furthermore, we expect that up to 20% of paired measurements may be missing due to non-compliance or technical problems.

Sample size calculations are based on approximate confidence intervals for Kendall's tau (35). The minimum number of measurements, to attain the required precision in the LE group is n=16; however, accounting for missing data we need to enroll 20 patients with LE and 200 patients overall. We thus expect to have 160 non-missing pairs of measurements overall, this allows us to determine Kendall's tau with 95% confidence interval from 0.426 to 0.567.

Of note, patients that are enrolled pre-operatively and subsequently undergo bilateral breast surgery, rendering them ineligible for the study, will not be counted towards the overall accrual goal of 200 subjects.

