### 6.4 Stratification factors and their impact on design

The analysis will be stratified on the time of follow-up, volumetric and BIS changes, as well as self-reported symptoms will be correlated at the corresponding time points.

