### 6.7 Analysis plan

The statistical analysis in this study will subsist in 1) calculating the Kendall's correlation coefficient with 95% confidence intervals for each time point, separately for all subjects and in the subgroup with  $RVC \geq 5\%$ , 2) plotting graphically the relationship between changes in arm volumes and BIS measurements, by time point, 3) calculate overall Kendall's tau stratifying by time point, i.e., evaluating concordant and discordant pairs within each time point only (35), 4) determining the change of BIS measurements

corresponding to RVC=5% of volumetric measurements, 5) calculating area under ROC curve, for predicting volumetric RVC $\geq$ 5% using BIS measurements, and tabulating diagnostic indices including specificity, sensitivity, positive prognostic value, 6) evaluating diagnostic characteristics of lymphedema diagnosis based on BIS using 3 sigma method, and 7) assessing the association between patient-reported symptoms and each measurement method (using area under ROC and other diagnostic criteria). We will also evaluate the statistical distribution of BIS measurements and based on the shape of the distribution determined if BIS changes are better captured as absolute or as relative differences.

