#### 6.8 Handling of missing data in the analysis

RVC for volumetric changes and a corresponding quantity for BIS changes will be calculated only with patients with measurements both at the baseline and during follow-up. Time points with missing data will be excluded from the evaluation of the correlation between volumetric and BIS changes and, separately, between BIS changes and patient-reported symptoms for those patients who complete the LEFT-BC questionnaire.

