**The following questions will ask you about arm, breast, and chest symptoms you have experienced in the last month:**

| Are you experiencing:         | None | Mild | Moderate | Severe | Not Applicable |
|-------------------------------|------|------|----------|--------|----------------|
| Tenderness?                   | 0    | 1    | 2        | 3      |                |
| Swelling?                     | 0    | 1    | 2        | 3      |                |
| Redness?                      | 0    | 1    | 2        | 3      |                |
| Firmness/tightness?           | 0    | 1    | 2        | 3      |                |
| Increased warmth in your arm? | 0    | 1    | 2        | 3      |                |
| Heaviness?                    | 0    | 1    | 2        | 3      |                |
| Numbness?                     | 0    | 1    | 2        | 3      |                |
| Stiffness?                    | 0    | 1    | 2        | 3      |                |

|                                    |   |   |   |   |  |
|------------------------------------|---|---|---|---|--|
| Aching?                            | 0 | 1 | 2 | 3 |  |
| Chest wall swelling?               | 0 | 1 | 2 | 3 |  |
| Breast swelling?                   | 0 | 1 | 2 | 3 |  |
| Other symptoms
Please describe: |   |   |   |   |  |

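### Section 6.7 analyses graded symptoms only through ROC area and diagnostic criteria, which need a yes/no cut the plan does not define; the symptom correlation foreseen in 6.4 and 6.8 is not carried through

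*Combined protocol and SAP*

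**What the plan says.** Section 2.1 lists as a primary objective: "To determine relationship between impedance ratios, relative volume changes (RVC), and self-reported symptoms". Section 6.1 repeats it as a primary aim, to "determine the relationships of BIS measurements to perometer measurements and to self-reported symptoms".

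Section 6.7 sets out the analysis in seven items. Item 7 is the only one that mentions symptoms: "assessing the association between patient-reported symptoms and each measurement method (using area under ROC and other diagnostic criteria". It does not say which variable is made binary, at what cut, or whether items are combined into a score.

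Two other sections bear on the point. Section 6.4 says that "volumetric and BIS changes, as well as self-reported symptoms will be correlated at the corresponding time points". Section 6.8 excludes time points with missing data from the evaluation of a correlation "between BIS changes and patient-reported symptoms for those patients who complete the LEFT-BC questionnaire". Neither names a coefficient, a symptom score or a confidence interval. Section 6.2 names Kendall's tau for the relationship between the two measurement methods, BIS and perometry.

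The LEFT-BC questionnaire (Appendix 2) asks about "arm, breast, and chest symptoms you have experienced in the last month". It has 11 named symptoms with the response columns "None | Mild | Moderate | Severe | Not Applicable", the first four scored 0 to 3.

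**The concern.** Symptoms are collected on four ordered grades, and RVC and BIS change are continuous. A yes/no cut of either side discards ordering that the trial has already paid to collect. The cost is a wider confidence interval and less chance of seeing an association, in one part of a primary objective. Because the cut is not stated, it could also be chosen after the data are seen, and the answer can change with it. Sections 6.4 and 6.8 suggest that a correlation is intended, yet the list that defines the analysis does not contain one for symptoms.

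**Working it through.** **1. The plan's own figures.** Section 6.2 gives no figure for symptoms. Its BIS-perometry chain reproduces: 16/(1 − 0.20) = 20 patients with lymphedema; 20/0.10 = 200 enrolled; 200 × 0.80 = 160 pairs. For tau = 0.50, an arcsine-scale interval with the exact bivariate-normal variance gives a minimum of n = 16 for a lower bound of 0.2, and 0.422 to 0.574 at n = 160. The plan states 0.426 to 0.567, slightly narrower, but the 0.42 target is met. Only n = 160 is carried forward.

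**2. What each method uses.** Sensitivity and specificity need both variables cut. ROC area needs one cut and keeps the ranks of the other. Somers' D of RVC with respect to symptom grade needs none. Among patient pairs that differ in grade, let C be the number concordant with RVC and Q the number discordant. Then D = (C − Q)/(C + Q), and (D + 1)/2 = C/(C + Q). With only two grades, C/(C + Q) is the ROC area, so ROC area is the special case in which the grades have been collapsed.

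**3. Size of the loss.** The documents give no symptom distribution and no symptom association, so the following are assumptions: one symptom, one observation per patient, n = 160, bivariate-normal latent variables, latent tau 0.15 (correlation sin(π × 0.15/2) = 0.233), two-sided 5% test, four grade distributions. Full grades were tested with Kendall's tau-b and the cut versions with the Mann-Whitney test, which is the test of ROC area. Power from 4,000 replicates:

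| Grades 0/1/2/3 (%) | Full grade | Any vs none | Moderate/severe vs less | Grade vs top 10% of RVC |
|---|---|---|---|---|
| 50/30/15/5 | 0.718 | 0.634 | 0.516 | 0.356 |
| 60/25/10/5 | 0.680 | 0.624 | 0.461 | 0.346 |
| 70/20/7/3 | 0.617 | 0.586 | 0.380 | 0.322 |
| 40/30/20/10 | 0.751 | 0.621 | 0.581 | 0.357 |

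Losses against the full grade, row by row, in percentage points:
- any vs none: 8.4, 5.6, 3.1, 13.0
- moderate/severe vs less: 20.2, 21.9, 23.7, 17.0
- RVC cut at its top 10%: 36.2, 33.4, 29.5, 39.4

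Independent re-runs agreed within simulation error. At latent tau 0.20 the losses were about 3-8, 11-26 and 34-39 points. A separate run at latent correlation 0.25 with grades 50/30/15/5 gave 0.80 for the full grade against 0.70, 0.59 and 0.38, and 0.25 with both variables cut.

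**4. Analytic cross-check.** Cutting one normal variable with a share p positive keeps φ(z)²/[p(1 − p)] of the information, where z is the cut-point and φ the normal density. This is 0.64 at p = 50%, 0.49 at 20% and 0.34 at 10%. The last value applies directly to cutting RVC. For symptoms the comparison is milder, because four grades are already coarser than a continuous variable.

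**5. Precision.** Section 6.2 designs for interval width, not for a test. Under the step 3 assumptions, the standard error of the concordance index was about 8-24% smaller than that of the any-vs-none ROC area, and about 28-41% smaller than that of the moderate/severe one. The index differs somewhat in value from those ROC areas, so power is the fairer net comparison.

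**6. Why Somers' D and not tau-b.** Between a continuous measure and a tied item with grade shares p, tau-b cannot exceed √(1 − Σp²). For the first distribution this is √(1 − 0.365) = 0.80; for the others it is 0.75, 0.68 and 0.84. The ceiling would move with symptom and visit. Somers' D with respect to the grade has no such ceiling.

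**The case against.** A reader might infer that symptoms will be analysed by ROC alone. The documents do not support that: 6.4 and 6.8 foresee a correlation. Items 1 and 3 of 6.7 also name no pair of variables, so tau could be read as extending to symptoms. What stands is that neither section names a coefficient, 6.2 ties tau to BIS and perometry, and the one item of 6.7 on symptoms names something else.

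A reader might also infer that much information is lost whatever the cut. That is not shown. ROC area keeps the ranks of the uncut variable, and any versus none costs only 3 to 13 points. The largest loss assumes that RVC is the variable cut and that 10% are positive among the analysed pairs. Section 6.2 gives 10% as the share who develop lymphedema with RVC of at least 5%, not the share at a given visit.

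Nor do the documents support saying that the three relationships could not be read side by side. Item 5 already gives a ROC area for BIS against RVC of at least 5%, so item 7 shares a scale with it.

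Finally, the study asks about detection and compares diagnostic criteria, and RVC of at least 5% is its operational definition of lymphedema (5.2, 5.3). ROC area and diagnostic indices answer that question and belong in the plan. The objection justifies keeping them, but not having them as the only specified analysis of a graded relationship.

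**Conclusion.** The point holds in a limited form. For the symptom part of a primary objective, 6.7 specifies only a method that needs an undefined cut, while the correlation promised elsewhere is left unspecified. Depending on the cut, the loss ranges from small (about 3 to 13 points of power) through moderate (about 17 to 24) to large (about 30 to 39).

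Every power and standard-error figure rests on assumed grade distributions, an assumed latent tau of 0.15, bivariate normality and single observations; only n = 160 and the 10% share come from the plan. The direction was the same in every scenario run. The planned analysis is not invalid. This is a gain in precision and a gap in specification, worth correcting because the remedy is cheap.

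**What to change.** Amend item 7 of section 6.7:

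- For the 11 symptoms graded 0-3, make the main estimate Somers' D, or equivalently the concordance index (D + 1)/2, of RVC and of BIS change with respect to symptom grade.
- Compute it within each time point, and overall stratified by time point as in item 3, with 95% confidence intervals. Treat Not Applicable as missing.
- State that this is the correlation meant in 6.4 and 6.8.
- Keep ROC area and diagnostic indices as secondary, with the variable to be cut and the cut-point stated in advance. Use them for the binary cording items and for the size and fit-change items, whose responses are not ordinal.

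The index reduces to the ROC area when the symptom is binary, so it stays on the scale of item 5.

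The cost is a short amendment and further runs of rank methods already needed for items 1 and 3; reference 35 concerns confidence intervals for Somers' D. No new data or visits are needed, so the closure of accrual is no obstacle. The downside is 11 × 2 = 22 more estimates per time point, to be reported as descriptive estimates with confidence intervals.

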#### 6.8 Handling of missing data in the analysis

RVC for volumetric changes and a corresponding quantity for BIS changes will be calculated only with patients with measurements both at the baseline and during follow-up. Time points with missing data will be excluded from the evaluation of the correlation between volumetric and BIS changes and, separately, between BIS changes and patient-reported symptoms for those patients who complete the LEFT-BC questionnaire.

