### *Perometer*

The perometer is a well-validated instrument for quantifying volume in a limb, and has been a regular part of the standard of care for MGH breast cancer patients since 2005. Patients are routinely measured (1) at diagnosis, (2) after surgery, (3) after chemotherapy, (4) after radiation, (5) at four to seven month follow-up visits that continue for five years, and (6) any time a patient reports with new symptoms of swelling or arm discomfort outside these time frames. The perometer provides highly reliable and valid arm volume measurements, with no physical discomfort or inconvenience to the patient. It utilizes infrared lamp-light receiver pairs contained within a frame which is moved along the extremity. As indicated by our preliminary analyses and the literature, the perometer calculates volume within 1% accuracy (33). This calculation of volume is accurate within a standard deviation of 8.9 ml and a .55% difference with repeated measurements (33). The perometer can give detailed information about arm volume in milliliters, the percent difference between the volumes of both arms, the location of the swelling in the arm as well as a follow-up clearly showing progression of the lymphedema over time.

Measurements of arm volume with the perometer will be taken pre- and post-operatively, as well as at screening visits per study design. All arm volume measurements will be converted to a percent RVC. The RVC calculation will indicate volume changes in the affected arm as compared to the baseline measurement. This value will indicate whether or not a patient is experiencing lymphedema for the purposes of this study and will determine patient eligibility for enrollment into Partners Protocol 08-308.

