### *Questionnaire*

The primary source of data on symptoms, functionality, arm use and quality of life will be derived from a questionnaire completed at each lymphedema assessment. Patients who are enrolled in the study will complete the questionnaire at their initial point of enrollment (after diagnosis and prior to definitive breast surgery), and at all subsequent assessments.

This questionnaire is currently being utilized as part of Partners' Protocols 08-540 and DFHCC Protocol #08-308 and as such has been completed by over 500 patients on protocol since 2009. It was developed to analyze symptoms, functionality, fear avoidance behavior, and quality of life. This questionnaire is referred to as the Lymphedema Evaluation Following Treatment for Breast Cancer Questionnaire (LEFT-BC), and it has been pilot tested for clarity, readability, and validity. This pilot testing was completed with a sample of 20 patients currently undergoing perometer measurements as a standard of care within the MGH Gillette Breast Center. After completion of the pilot, adjustments were made to the questionnaire to increase clarity and readability. The complete questionnaire is included in Appendix 2.

In order to minimize respondent burden the questionnaire was limited to 6 written pages and took between 5-12 minutes to complete during the pilot study. We will utilize tablet style PCs for questionnaire completion within the clinic. [name] and [name], MS developed the LEFT-BC Questionnaire program by formatting the

questionnaires for the tablet PCs, and a corresponding database for data logging. The questionnaires will be completed by patients in a point and click manner. In the event that tablet PCs are not available, paper copies of the questionnaire will be available for participant visits. Questionnaire responses from paper based questionnaires will be manually entered into the database.

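### The symptom analyses set baseline-corrected RVC and BIS changes against same-visit symptoms and state no use of the pre-operative LEFT-BC, so persisting unrelated symptoms could dilute both associations

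*Combined protocol and SAP*

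**What the plan says.** **Device measures.** Under Perometer in 5.2, "The RVC calculation will indicate volume changes in the affected arm as compared to the baseline measurement". For BIS, 6.1 says that "we will use a similar formula for quantification of BIS changes after evaluating the statistical distribution of BIS measurements". Section 6.8 ties both to the pre-operative reading: "RVC for volumetric changes and a corresponding quantity for BIS changes will be calculated only with patients with measurements both at the baseline" (a later reading is needed too).

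**Symptoms.** Section 6.4 has "volumetric and BIS changes, as well as self-reported symptoms will be correlated at the corresponding time points". Step 7 of 6.7 plans "assessing the association between patient-reported symptoms and each measurement method (using area under ROC and other diagnostic criteria"). The missing-data rule in 6.8 speaks of an evaluation "between BIS changes and patient-reported symptoms for those patients who complete the LEFT-BC questionnaire". None of these sections gives a symptom change score, a definition of a new symptom, or a baseline symptom term. Section 6.8 requires a baseline for RVC and BIS and says nothing equivalent for symptoms.

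**What is collected.** Under Questionnaire in 5.2, patients "will complete the questionnaire at their initial point of enrollment", which is placed after diagnosis and before definitive surgery, and again at every later assessment. In Appendix 2 the severity items (tenderness, numbness, stiffness, aching and others) are scored 0 to 3 for the last month. Six other items ask whether arm, shoulder or neck size, or sleeve, cuff or ring fit, has changed, also over the last month.

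**The concern.** The relationship between impedance ratios, RVC and self-reported symptoms is a primary objective (2.1). Section 1.2.4 justifies the study partly by the lack of pre-surgical assessment in earlier work. The planned symptom comparison removes each patient's starting point from the device side and, as worded, leaves it in on the symptom side.

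Stiffness, aching or numbness can be present before surgery for reasons unrelated to the arm's fluid. If such a symptom persists, the patient counts as symptomatic at follow-up whatever the limb has done. This pulls the AUC towards 0.5 for perometry and BIS alike. The trial could then report that the devices track symptoms weakly when they track newly arising symptoms better.

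The questionnaire wording does not correct for this. Assessments are 4 to 12 months apart in the first 24 months after treatment and up to 20 months apart later (5.4), so a question about change in the last month does not measure change since before surgery.

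**Working it through.** **1. The plan's own figures.** The plan gives none for the symptom analysis. Its precision figures (6.2) concern Kendall's tau between RVC and BIS. They reproduce with tanh(atanh(0.5) ± 1.96·√(0.36/(n−4))):
- n = 160 gives 0.426 to 0.567, as stated.
- n = 16 gives a lower bound of 0.207, and 16 is the smallest n that reaches 0.2.
- 16/0.8 = 20 and 160/0.8 = 200.

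The constant 0.36 was back-solved from the stated interval; the documents do not give it. The sample size does not depend on the symptom analysis, so this point leaves it unchanged.

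**2. Is there dilution? A yes/no symptom.** All inputs here are assumptions, because the documents give neither the prevalence nor the persistence of pre-operative symptoms. Limb change L is standard normal. The device reading is 0.8L + 0.6·noise. A new symptom occurs when 0.7L + √0.51·noise exceeds 0.8416, which is about 20% of patients. Pre-existing symptoms are independent of L. With no pre-existing symptoms the AUC of the device reading for the symptom is 0.778.

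| Pre-operative prevalence | Same-visit symptom, all persist | Half persist | None persist |
|---|---|---|---|
| 5% | 0.731 | 0.752 | 0.778 |
| 10% | 0.699 | 0.731 | 0.778 |
| 20% | 0.655 | 0.698 | 0.778 |
| 30% | 0.626 | 0.673 | 0.778 |
| 40% | 0.606 | 0.655 | 0.778 |

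Analysing only patients without the symptom before surgery restores about 0.778. Keeping all patients and counting a symptom only if present now and absent before gives about 0.75 to 0.77.

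**3. A continuous score.** Assumed model: baseline = trait + noise (SD 0.7); follow-up = trait + positive part of latent swelling (SD 1) + noise (SD 0.7); RVC-positive = top 10% of swelling measured with noise of SD 0.7. Adjustment is the follow-up score minus the regression slope times the baseline score. AUC for RVC-positive:

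| Trait SD | Same-visit score | Baseline-adjusted | Loss without adjustment |
|---|---|---|---|
| 0.2 | 0.814 | 0.815 | 0.001 |
| 0.5 | 0.79 | 0.80 | 0.01 |
| 1.0 | 0.73 | 0.78 | 0.05 |
| 1.5 | 0.68 | 0.77 | 0.09 |

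The AUCs depend on the swelling noise. At trait SD 1.0, noise SDs of 0.3, 0.5 and 0.7 give 0.78, 0.76 and 0.73 for the same-visit score and 0.84, 0.81 and 0.78 after adjustment, so the gap stays at about 0.05 to 0.06. With the score cut to 0-3 (noise SD 0.5), adjustment still leads: 0.806 against 0.794, 0.764 against 0.734, and 0.729 against 0.681 at trait SD 0.5, 1.0 and 1.5.

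**4. Subtraction or adjustment?** In a separate run, Kendall's tau between the device reading and the symptom score was:

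| Baseline to follow-up correlation of the part unrelated to lymphedema | Level | Raw change | Adjusted |
|---|---|---|---|
| 0.2 | 0.334 | 0.282 | 0.338 |
| 0.5 | 0.331 | 0.329 | 0.362 |
| 0.8 | 0.332 | 0.426 | 0.437 |

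Subtraction beats the level only above a correlation of about 0.5. Adjustment was not worse than the level in any of these runs.

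**5. Against sampling error.** The plan expects 160 evaluable pairs, of which 10%, or 16, have lymphedema and 144 do not. The Hanley-McNeil variance is [A(1−A) + 15(Q₁−A²) + 143(Q₂−A²)]/(16·144), with Q₁ = A/(2−A) and Q₂ = 2A²/(1+A).
- A = 0.80: (0.16 + 0.40 + 10.17)/2304 = 0.00466; half-width 1.96·√0.00466 = 0.13.
- A = 0.69: (0.21 + 0.76 + 12.49)/2304 = 0.00584; half-width 0.15.

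The losses in step 3 are smaller than one such half-width.

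**The case against.** **The plan does not say that levels will be used.** A reader might infer that it prescribes uncorrected symptom levels. It does not. No section defines the symptom variable, and the sentence in 6.8 is a missing-data rule. The wording is loose elsewhere too: step 5 of 6.7 speaks of BIS measurements where BIS changes appear to be meant, and step 7 does not say change for the devices either. Section 6.1 lists LEFT-BC data as endpoint data without excluding the pre-operative form. This stands. What remains is that three sections put symptoms beside device changes and none gives the baseline questionnaire a role.

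**The 6.8 sentence covers BIS only.** A reader might take it as settling both devices. It does not. The perometry half rests on 6.4 and on step 7 of 6.7, which do cover both.

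**Six items are not levels.** The size and fit items ask about change and bear closely on swelling. Adjusting them for a pre-operative answer has no clear meaning. This stands, and the fix leaves them out.

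**Same-visit symptoms are a fair question.** Objective 2.1 names self-reported symptoms, not new ones, and how current symptoms relate to measured swelling is a legitimate diagnostic question. This also stands, and is why the unadjusted result should be kept beside the adjusted one.

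**The effect may be small.** Primary lymphedema, prior regional surgery or radiation, and current cellulitis are excluded (3.2.4, 3.2.5, 3.2.8). Baseline follows biopsy (5.1), and transient biopsy symptoms that resolve cause no dilution. Symptoms produced by treatment arise after baseline, and baseline adjustment cannot remove them. All of this limits the size but does not reverse the direction.

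**Conclusion.** The point holds as a gap with a known direction and an unknown size. On the plain reading of 6.4, 6.7 (step 7) and 6.8, baseline-corrected device changes are related to same-visit symptoms with no stated use of a pre-operative questionnaire that is already collected. Unrelated symptoms that persist would then weaken the association for both devices.

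The size rests wholly on assumptions. There is no loss if none of the pre-existing symptoms persist, and almost none at a trait SD of 0.2. For trait SDs of 0.5 to 1.5, with swelling noise of SD 0.7, the AUC loss is about 0.01 to 0.09. The yes/no model gives larger losses, but only if pre-existing symptoms are common and mostly persist.

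A reader might go further and conclude that the symptom results will be misleading or that the trial is undersized. The documents support neither: they give no figure for pre-operative symptoms, and the sample size rests on tau between RVC and BIS. The change is worth making because it serves a primary objective at almost no cost.

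**What to change.** In step 7 of 6.7 and in 6.8:
- **Define the symptom variable**, item by item or as a score built from the 0-3 severity items.
- **Adjust it** for the same patient's pre-operative value of the same item or score, with baseline as a covariate or by a baseline-adjusted ROC curve. Do not use raw subtraction. Report the unadjusted same-visit association beside it.
- **For yes/no symptoms**, report new symptoms among patients without the symptom before surgery, as a supporting analysis.
- **Leave the six size and fit items unadjusted** and analyse them as reported.

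The cost is a few sentences and one covariate already collected, with no change in sample size. Patients without a pre-operative questionnaire drop out of the adjusted analysis, in line with the baseline rule that 6.8 already applies to RVC and BIS. The new-symptom analysis will have fewer lymphedema cases than the roughly 16 evaluable ones expected, so it should stay supporting. If baseline adjustment is already intended, one sentence saying so is enough.
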